| | 
dexamethasone 4 mg IV or equivalent)
 
 • Vital signs (pulse rate, respiratory rate, blood pressure, and temperature) should be measured within 60 minutes prior to the infusion. • MGC018 should be infused over 60 minutes. Up to 10 additional minutes of infusion time is permitted to allow for flushing the IV line. • If clinically indicated, vital signs should be measured every 15 (\pm 5) minutes during the infusion. • Patients should be informed about the possibility of delayed post-infusion symptoms and instructed to contact their study physician if they develop such symptoms. | 
 • Vital signs should be measured within 60 minutes prior to the infusion. • MGC018 should be infused over 60 minutes (\pm 10 minutes) if the previous infusion was tolerated without an IRR, or 60 (\pm 15) minutes if the patient experienced an IRR with the previous infusion. • If clinically indicated, vital signs should be measured during the infusion and at 30 (\pm 10) minutes after the infusion. |
| Observation period after infusion of MGC018 | 
 • After the infusion of MGC018, the patient begins a 60-minute observation period. • Vital signs should be recorded at 30 \pm 10 minutes after the infusion of MGC018. • Patients will be informed about the possibility of delayed post-infusion symptoms and instructed to contact their study physician if they develop such symptoms. | 
 • If the patient tolerated the previous MGC018 infusion well without infusion-associated adverse events, no observation period is needed. • If the patient experienced infusion-associated adverse events in the previous infusion, an observation period of 60 minutes should occur. • If clinically indicated, vital signs should be recorded at 30 (\pm 10) minutes after the infusion of MGC018. |

Refer to the pharmacy manual for detailed instructions on drug preparation, storage, and administration.

4.2.3 **Dose modification and management of adverse events**

4.2.3.1 **General notes regarding dose modifications & delays**

Reasons for dose delays, supportive measures taken, and subsequent outcome will be documented in the patient's chart and recorded on the eCRF. The severity of adverse events will be graded according to the NCI CTCAE v5.0 grading system.

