| Grade 3 | 
 • Hold or permanently discontinue MGC018 • Consider hospitalization and rheumatology consultation • Begin corticosteroids 2 to 4 mg/kg of oral or IV methylprednisolone or equivalent per day divided twice daily. Continue IV methylprednisolone 2 mg/kg/day for a total of 5 days then switch to oral prednisolone 1 mg/kg/day x 3 days, then reduce to 60 mg/day prednisolone. Reduce prednisolone dose by 10 mg every 5-7 days (as toxicity allows) until dose is 10 mg/day. Once steroid dose is 10 mg/day, reduce by 5 mg every 5-7 days then stop. • Consider infliximab • If not responding within 14 days, consider use of disease modifying antirheumatic drugs e.g. sulfazine, methotrexate. • On resuming MGC018, reduce dose by one dose level after first and second occurrences • Discontinue MGC018 after third occurrence |
| Grade 4 | 
 • Treat as grade 3 • On resuming MGC018 reduce dose by two dose levels after first occurrence • Discontinue MGC018 after second occurrence |

INFUSION-RELATED REACTIONS

Premedications at least 30 minutes prior to each infusion of MGC018 include: acetaminophen 650 to 1000 mg PO or ibuprofen 400 mg PO, diphenhydramine 50 mg PO or IV or equivalent H1 antagonist, famotidine 40 mg PO or 20 mg IV or equivalent H2 antagonist, corticosteroid (e.g dexamethasone 4 mg IV or equivalent).

For subsequent administration of MGC018, participants who had infusion reactions that were not adequately or only moderately controlled, other medications may also be considered as part of the pre-medication regimen for subsequent doses.

Guidelines for medical management of IRRs during Cycle 1 are provided in Table 19. For subsequent cycles, IRRs should be managed according to institutional guidelines.

Table 19. Management Guidelines for Infusion-Related Reactions

| Event | Management |
|-------------------|--|

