| IRR, Grade 1 | 
 • Reduce infusion rate to half the rate being given at the time of event onset. • Monitor the participant for worsening of condition • After the event has resolved, the sponsor-investigator should wait for 30 minutes while delivering the infusion at the reduced rate. • If the infusion is tolerated at the reduced rate for 30 minutes after symptoms have resolved, the infusion rate may be increased to the original rate. • Prophylactic premedication with antipyretics, antihistamines, and/or analgesics should be given prior to all subsequent infusions |
| IRR, Grade 2 | 
 • Interrupt infusion. • Administer aggressive symptomatic treatment (e.g., oral or IV antihistamine, anti-pyretic medication, glucocorticoids, epinephrine, bronchodilators, oxygen, IV fluids). • After symptoms have resolved to baseline or decreased to grade 1, resume infusion at half the rate being given at the time of event onset. • If the infusion is tolerated at reduced rate for 30 minutes, rate may be escalated to original rate after 30 minutes as tolerated • For subsequent infusions, prophylactic administration of premedication with antihistamines, anti-pyretics, and/or analgesics and monitor closely for IRRs. Corticosteroids may also be added (dexamethasone 10 mg IV or hydrocortisone 25 to 100 mg IV or higher) |
| IRR, Grade 3 or 4 | 
 • Stop infusion. Do not flush tubing. • Administer aggressive symptomatic treatment (e.g., oral or IV antihistamine, anti-pyretic medication, glucocorticoids, epinephrine, bronchodilators, oxygen, IV fluids). • If grade 3 infusion reaction occurs, discontinue treatment for that day. If symptoms have resolved to baseline within 12 hours, MGC018 may be infused the next day with premedication and for any subsequent doses with antipyretics, antihistamines, and corticosteroids. • Participants who have a grade 3 infusion reaction that does not resolve within 12 hours should not receive further treatment with MGC018. • Participants who experience a second grade 3 infusion reaction at time of rechallenge with MGC018 will permanently discontinue treatment with study drugs. • Participants who have a grade 4 infusion reaction will not receive further treatment with MGC018 • Reports as an IRE within 24 hours and event as SAE |

IRR = infusion-related reaction, IRE=infusion related event, SAE=serious adverse event

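### After an infusion reaction, Table 3's 60 (±15) minute window permits a 45-minute infusion, the fastest in the protocol; the window should run only towards slower

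*Combined protocol and SAP*

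**What the plan says.** Table 3 in Section 4.2.2.1 gives three infusion times.

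- First infusion: 60 minutes. The only tolerance is upward: "Up to 10 additional minutes of infusion time is permitted to allow for flushing the IV line".
- Later infusion after a tolerated one: 60 minutes, plus or minus "10 minutes) if the previous infusion was tolerated without an IRR".
- Later infusion after a reaction: 60 minutes, plus or minus "15) minutes if the patient experienced an IRR with the previous infusion".

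Below the table the protocol adds: "Refer to the pharmacy manual for detailed instructions on drug preparation, storage, and administration". That manual is not among the documents reviewed.

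Table 19 in Section 4.2.3.2 covers reactions in Cycle 1; reactions in later cycles are left to institutional guidelines. For grades 1 and 2 it halves the rate of the infusion in progress and lets the rate return to normal. The grade 2 row says: "If the infusion is tolerated at reduced rate for 30 minutes, rate may be escalated to original rate after 30 minutes as tolerated". For grade 3 the infusion stops for the day, and then: "If symptoms have resolved to baseline within 12 hours, MGC018 may be infused the next day with premedication". The grade 3 row gives no rate or duration for that next-day infusion.

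**The concern.** A wider window after a reaction would be expected to give room to slow down. As written it also gives room to speed up, and more room than a patient who tolerated the drug is given. The permitted minimum falls from 60 minutes (first infusion) to 50 (after tolerance) to 45 (after a reaction), which is the reverse of a cautious order.

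This is a patient-safety matter. Infusion-related reactions are among the risks listed in Section 5.1.1, and in Table 19 a second grade 3 reaction at rechallenge ends treatment permanently. The trial runs at several sites and may add more, so the written window is the shared rule.

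**Working it through.** **Inputs.** Starting dose 2.0 mg/kg (Section 4.2.2.1) and the three infusion times in Table 3. The calculation assumes an even rate and the same dose at both infusions.

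**Formulas.** Shortest time = target minus tolerance; longest time = target plus tolerance. Rate relative to a 60-minute infusion = 60 / duration.

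| Situation | Permitted minutes | Fastest relative rate | Slowest relative rate |
|---|---|---|---|
| First infusion | 60 to 70 (the extra 10 for flushing) | 60/60 = 1.00 | 60/70 = 0.86 |
| Later, previous tolerated | 60 − 10 = 50 to 60 + 10 = 70 | 60/50 = 1.20 | 60/70 = 0.86 |
| Later, previous reaction | 60 − 15 = 45 to 60 + 15 = 75 | 60/45 = 1.33 | 60/75 = 0.80 |

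**In dose terms.** 2.0/60 = 0.0333 mg/kg/min at the first infusion; 2.0/45 = 0.0444 mg/kg/min at the post-reaction lower edge. For an assumed weight of 60 to 100 kg (120 to 200 mg), that is 2.00 to 3.33 mg/min against 2.67 to 4.44 mg/min. In the first 30 minutes a patient receives 30/60 = 50% of the dose at 60 minutes, but 30/45 = 67% at the 45-minute edge.

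**Against the fastest infusion allowed after tolerance.** 50/45 = 1.11.

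**How the ratio depends on what came before.** The figure of 1.33 holds when the infusion that caused the reaction was planned for 60 minutes, as every first infusion is. If it was a later infusion run over 50 minutes, the ratio is 1.11. If the dose had been reduced to 1.5 mg/kg, the 45-minute edge gives 1.5/45 = 0.0333 mg/kg/min, equal to the first infusion; Table 19 does not call for a dose reduction after a reaction.

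**Does any other text restrict the window to slowing?** The introduction to Section 4.2.2.1, the infusion-reaction text and Table 19 in Section 4.2.3.2, and the dosing conditions in Section 4.4 contain no such limit. Table 19's half-rate steps apply to the infusion under way in Cycle 1, not to the next complete dose.

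**Next-day infusion after grade 3.** The text does not say which column of Table 3 covers it. Read as a later infusion it would run 45 to 75 minutes; read as a first infusion, 60 minutes plus up to 10 for flushing.

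**The case against.** The strongest reply is that a tolerance is not an instruction. The target after a reaction is still 60 minutes, nobody is told to go faster, and the same window allows 75 minutes, slower than the 70 allowed after a tolerated infusion. A clinician would have to choose the fast edge for a patient known to have reacted. Section 4.4 makes each dose depend on an acceptable clinical assessment, infusions are given in a monitored setting, and a 60-minute observation period follows an earlier reaction. All of this stands and keeps the point modest. It does not explain why the lower edge should fall after a reaction.

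A reader might infer three stronger claims, which the documents do not support.

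- *That Table 3 is the only rate rule for a patient who has reacted.* Table 19 has half-rate rules for grades 1 and 2 within the ongoing infusion. Table 3 is the rule for the next complete dose, and after a reaction in a later cycle institutional guidelines also apply.
- *That the silent grade 3 row calls for a mandatory half-rate start.* The pharmacy manual is cited for administration and may set a rate, so its absence from the plan as a whole is not shown. A half-rate start would be borrowed from rules for an infusion in progress.
- *That grade 3 premedication is no stronger than on Day 1, so a higher steroid dose should be required.* The classes do overlap. Routine premedication already reads "Premedications at least 30 minutes prior to each infusion of MGC018 include: acetaminophen 650 to 1000 mg PO or ibuprofen 400 mg PO", followed by antihistamines and "corticosteroid (e.g dexamethasone 4 mg IV or equivalent". But the grade 3 row lists corticosteroids outright, where the grade 2 row makes them optional. Section 4.2.2.1 also gives prednisone 40 mg twice daily for three days from the evening after each infusion. The protocol does not say whether a stopped infusion triggers that course; if it does, a next-day infusion falls within it. A larger mandatory dose is therefore a clinical preference.

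**Conclusion.** The point holds for Table 3. The post-reaction window permits a 45-minute infusion: 1.33 times the 60-minute first-infusion rate and 1.11 times the fastest rate permitted after tolerance, for the same dose given evenly. It is a permission at the edge of a tolerance, not a planned regimen, and the wider window may have been meant only as room to slow down. The documents give no reaction frequency and the trial has at most 17 patients, so the number affected cannot be stated and is probably small.

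The missing rate in Table 19's grade 3 row is a matter for clarification, subject to what the pharmacy manual says. Nothing here bears on ORR, the Simon boundaries, type I error or power.

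**What to change.** In Table 3, make the post-reaction window one-sided: not shorter than 60 minutes and up to at least 75, longer if the pharmacy manual's in-use limits allow. The upper limit deserves that check because Section 9.2 does not allow prospective requests to deviate, so a clinician who wants to go slower needs the room in writing.

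In the grade 3 row of Table 19, add that this same window applies to the next-day re-infusion, or cite the pharmacy manual's rate if it sets one. No mandatory half-rate start or higher steroid dose is proposed.

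The cost is one table cell, one clarifying sentence and a check against the pharmacy manual. For the few patients who react, it means up to 60 − 45 = 15 minutes more than the present lower edge, and nothing against the 60-minute target.

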4.2.4 IMP handling and accountability

All IMPs required for completion of this study will be provided by MacroGenics. The study site (i.e., investigator or other authorized personnel [e.g., pharmacist]) is responsible for maintaining records of IMP delivery to the site, IMP inventory at the site, IMP use by each patient, and disposition or return of unused IMP, thus enabling reconciliation of all IMP received, and for ensuring that patients are provided with doses specified by the protocol.

The study site should follow all instructions included with each shipment of IMP. The study site will acknowledge receipt of IMPs supplied by MacroGenics, using the IxRS to confirm the shipment condition and content. Any damaged shipments will be replaced. The investigator or designee must confirm that appropriate temperature conditions have been maintained during transit for all IMPs received and that any discrepancies have been reported and resolved before use of the IMPs. All IMPs must be stored in a secure, environmentally controlled, and monitored (manual or automated) area in accordance with the labeled storage conditions, with access limited to the investigator and authorized staff.

Only patients enrolled in the study may receive IMPs, and only authorized staff may supply or administer IMPs.

IMPs will either be disposed of at the study site according to the study site's institutional standard operating procedure or be returned to MacroGenics with the appropriate documentation. The site's method of destroying MacroGenics-supplied IMPs must be agreed to by MacroGenics. The site must obtain written authorization from MacroGenics before any MacroGenics-supplied IMP is destroyed, and IMP destruction must be documented on the appropriate form.

Accurate records of all IMPs received at, dispensed from, returned to, and disposed of by the study site should be recorded on the drug accountability log.

Refer to the pharmacy manual and the MGC018 IB for information on IMP handling, including preparation and storage, and accountability.

4.3 CONCOMITANT THERAPY

Concomitant therapy consists of any medication (e.g., prescription drugs, over-the-counter drugs, vaccines, herbal or homeopathic remedies, nutritional supplements) used by a patient in addition to protocol-mandated treatment from 7 days prior to initiation of study treatment to the treatment discontinuation visit. All such medications should be reported to the investigator and recorded in the patient's medical records as well as on the Concomitant Medications eCRF.

4.3.1 Prohibited therapy

Use of the following concomitant therapies is prohibited as described below:

- Concomitant therapy intended for the treatment of cancer (including, but not limited to, chemotherapy, hormonal therapy, immunotherapy, radiotherapy, and herbal therapy), whether health authority–approved or experimental, is prohibited during study treatment, until disease progression is documented and the patient has discontinued study treatment.
- Live, attenuated vaccines (e.g., FluMist®) are prohibited within 4 weeks prior to initiation of study treatment, during study treatment, and for 5 months after the last dose of study treatment.

- Available vaccines for COVID-19 will be permitted at any time while a patient is enrolled on study but preferably not administered on same day as study drug infusion to avoid potential for overlapping immune-related reactions.

4.4 STUDY ASSESSMENTS

The schedule of activities to be performed during the study is provided in Appendix 1. All activities must be performed and documented for each patient. Patients will be closely monitored for safety and tolerability throughout the study. Patients should be assessed for toxicity prior to each dose; dosing will occur only if the clinical assessment and local laboratory test values are acceptable.

All treatment visits must occur ± 3 days from the scheduled date unless otherwise noted (see Appendix 1). All assessments should be performed on the day of the specified visit unless a time window is specified. Patients must be assessed for toxicity prior to each dose; dosing will occur only if the clinical assessment and local laboratory test values are acceptable. Assessments scheduled on the day of study treatment administration should be performed prior to dosing, unless otherwise specified.

Laboratory tests performed within 14 days of Day 1 of Cycle 1 and within 3 days of Day 1 of subsequent cycles do not need to be repeated prior to therapy administration.

If a holiday, weekend, or other event precludes scheduled dosing, dosing may be postponed to the soonest following date, with subsequent dosing continuing on a 28-day schedule. If treatment is postponed for fewer than 3 days, the patient can resume the original schedule.

4.4.1 Informed consent forms (ICFs)

Written informed consent for participation in the study must be obtained before performing any study-related procedures. ICFs for enrolled patients and for patients who are not subsequently enrolled will be maintained at the study site.

4.4.2 Medical history, concomitant medication, and demographic data

Medical history, including clinically significant diseases, surgeries, cancer history (including prior cancer therapies and procedures), reproductive status, smoking history, and use of alcohol and drugs of abuse, will be recorded at baseline. In addition, all medications (e.g., prescription drugs, over-the-counter drugs, vaccines, herbal or homeopathic remedies, nutritional supplements) used by the patient within 7 days prior to initiation of study treatment will be recorded. At the time of each follow-up physical examination, an interval medical history should be obtained and any changes in medications and allergies should be recorded. Demographic data will include age, sex, and self-reported race/ethnicity.

4.4.3 ECOG performance status

Performance status will be measured using the ECOG Performance Status scale at the timepoints specified in the schedule of activities in Appendix 1.

4.4.4 Physical examinations

A physical examination performed at screening, should include an evaluation of the dermatologic, cardiovascular, respiratory, and neurologic systems. Other systems should be examined as clinically indicated. Any abnormality identified at baseline should be recorded in the patient's medical records.

Limited, symptom-directed physical examinations should be performed as clinically indicated during subsequent visits. Changes from baseline abnormalities should be recorded in patient notes. New or worsened clinically significant abnormalities should be recorded as adverse events on the Adverse Event eCRF.

4.4.5 Tumor response evaluations

Any evaluable or measurable disease must be documented at screening and re-assessed at each subsequent tumor evaluation. Tumor assessments performed as standard of care prior to obtaining informed consent and within 28 days prior to initiation of study treatment do not have to be repeated at screening. Measurable disease is a requirement for study inclusion and response will be assessed by the investigator per RECIST v1.1 at baseline. Patients will undergo tumor assessments every 2 cycles while on study until radiographic disease progression per RECIST v1.1 or loss of clinical benefit as determined by the investigator. Tumor assessments should be performed during the last week of the cycle and before the start of treatment in the next cycle (see Appendix 1). At the investigator's discretion, tumor assessments may be repeated at any time if progressive disease is suspected.

Screening assessments must include CT or magnetic resonance imaging (MRI) scans (with IV contrast unless contraindicated) of the chest, abdomen, and pelvis. If a positron emission tomography (PET)/CT scan is performed, the CT portion of the study must be consistent with the standards of a full-contrast diagnostic CT scan unless IV contrast is contraindicated. A CT scan with contrast or MRI scan of the head must be done at screening to evaluate for the presence of CNS metastases in all patients (MRI preferred). An MRI scan of the head is required to confirm or refute the diagnosis of CNS metastases at baseline in the event of an equivocal CT scan. At the investigator's discretion, other methods of assessment of measurable disease as per RECIST v1.1 may be used.

All measurable and evaluable lesions identified at baseline should be re-assessed at each subsequent tumor evaluation. The same radiographic procedures used to assess disease sites at screening should be used for subsequent tumor assessments (e.g., the same contrast protocol for CT scans). Stable brain metastases must be evaluated with each subsequent tumor assessment with the same radiographic procedure as the baseline study. Patients without brain metastases do not need brain scans for subsequent on-treatment tumor assessment unless clinically warranted or part of standard-of-care treatment.

4.4.6 Laboratory, biomarker, and other biological samples

Samples for the following laboratory tests must be reviewed prior to dosing. See Appendix 1 for specifics related to which lab tests are required at specific time points during study ("screening" vs "on treatment", etc.):

- Hematology: WBC count, RBC count, hemoglobin, hematocrit, platelet count, and differential count (neutrophils, eosinophils, basophils, monocytes, lymphocytes, other cells).
- Chemistry panel (serum or plasma): bicarbonate or total carbon dioxide (if considered standard of care for the region), sodium, potassium, chloride, glucose, BUN or urea, creatinine, total protein, albumin, phosphorus, calcium, total bilirubin, alkaline phosphatase, ALT, and AST.
- Coagulation: INR, and aPTT (screening only).
- Thyroid function testing: thyroid-stimulating hormone (TSH), free triiodothyronine (T3) (or total T3 for sites where free T3 is not performed), and free thyroxine (also known as T4) at screening only. Repeat thyroid function testing as clinically indicated.

- Pregnancy test

All women of childbearing potential will have a serum pregnancy test at screening, and during the study, urine pregnancy tests will be performed at every cycle and after study treatment is discontinued. If a urine pregnancy test is positive, it must be confirmed by a serum pregnancy test.

A woman is considered to be of childbearing potential if she is postmenarchal, has not reached a postmenopausal state (≥ 12 continuous months of amenorrhea with no identified cause other than menopause), and has not undergone surgical sterilization (removal of ovaries and/or uterus).

The following samples will be sent to the PI or a designee for analysis or banked for subsequent analysis:

- Peripheral blood to be obtained on day 1 of cycle 1, day 1 of cycle 3, and at progression
- Prior to treatment initiation, tumor tissue will be obtained following progression on most-recent therapy for determination of biomarker status including exploratory correlative analyses. Please refer to the lab manual for details. **If a biopsy is not feasible and/or safe, it may be waived after discussion with the principal investigator.** In this case, we will obtain archival tissue if available.

For sampling procedures, storage conditions, and shipment instructions, see the laboratory manual.

Should a patient withdraw from the study, samples collected prior to the date of withdrawal may still be analyzed, unless the patient specifically requests that the samples be destroyed or local laws require destruction of the samples. However, if samples have been tested prior to withdrawal, results from those tests will remain as part of the overall research data.

Personnel performing laboratory analysis or biostatistics will only have access to random specimen codes and/or study subject ID numbers and not specific identifiers.

Given the complexity and exploratory nature of exploratory biomarker analyses, data derived from these analyses will generally not be provided to patients unless required by law and may be disclosed to third parties only as permitted by the ICF (or separate authorization for use and disclosure of personal health information) signed by the patient. The aggregate results of any conducted research will be available in accordance with the effective investigator policy on study data publication.

